15. WITHDRAWAL OF PARTICIPANTS

Subjects are free to withdraw from participation in the study at any time upon request.

Subjects who sign the informed consent form and who do not attend the workshop will be replaced. Subjects who sign the informed consent form, and who attend some or all of the workshop, but do not complete surveys or screening, or are withdrawn or discontinued from the study, will not be replaced.

16. DATA MANAGEMENT AND CONFIDENTIALITY

16.1 Project Data Collection

Standardized data collection forms (e.g., source documents, standardized assessment forms, etc.) are used to ensure data collected are consistent and compliant with the protocol and IRB application.

Data collection is the responsibility of study team members under the supervision of the Principal Investigator (PI). The PI is responsible for ensuring the accuracy, completeness, legibility, and timeliness of the recorded and reported data.

All data collection forms must be completed in a legible manner; any missing data will be explained. Data entry errors will be corrected with a single line through the incorrect entry and the correct data is entered above/near the correction. All changes will be initialed and dated.

16.2 Data Storage and Maintenance

Data will be stored in compliance with HIPAA regulations on encrypted UW research servers in the Department of Family Medicine and Community Health. All records including study enrollment information will be housed in compliance with regulations indefinitely until the analysis is complete. The process of destroying of these records post-analysis will comply with applicable UW or policies for research records.

The study ID, date of workshop attendance, age, zipcode, type of screening done, and screening results will be stored in REDCap Institute for Clinical and Translational Research (ICTR). Portable devices will be used to access secure web-based application of ICTR's RedCap. No data will be stored locally on the device. Only encrypted devices will be used.

Research Electronic Data Capture (REDCap) is a largely self-service, secure, web-based application for building and managing data collection forms. REDCap provides data management functionality by allowing the development of instrument and surveys to support data capture for research studies.

Post-workshop survey results will be stored in Qualtrics and not linked to study ID, results will be entirely anonymous. Paper copies of the intake form will be stored in a locked location at the Milwaukee Consortium for Hmong Health.

16.3 Confidentiality

There is a slight risk of loss of confidentiality of participant information to subjects enrolled on study. Records will be linked to study ID. Participant identification information will be stored separately and maintained with MCHH for purposes of contacting follow up results. Any information regarding participations will be kept confidential, and to the extent permitted, will not be publicly available. Information collected will be stored on secure, password-protected electronic systems and access will be limited to those involved directly on study.

17. PROVISIONS TO PROTECT THE PRIVACY INTERESTS OF PARTICIPANTS

Subject confidentiality and privacy are strictly held in trust by the participating investigators, their staff, and the sponsor(s) and their agents. This confidentiality is extended to cover testing of biological samples in addition to the demographic information relating to subjects. Therefore, the study protocol, documentation, data, and all other information generated will be held in strict confidence.

All research activities will be conducted in as private a setting as possible. Individual rooms will be available at the research site for answering intake questions, obtaining informed consent, survey data collection, and for sample collection. During workshops, participants will be asked to not to disclose any comments, questions, or feedback provided by other participants to anyone outside of the study setting.

All study staff engaged in the conduct of this project have completed training on the protection of human subjects and the Health Insurance Portability and Accountability (HIPAA) Privacy Rule. In addition, all key personnel (i.e., Principal Investigator, individuals involved in identifying/recruiting subjects, obtaining informed consent, or interacting and intervening with subjects) have undergone Good Clinical Practice (GCP) training.

Information about study subjects will be kept confidential and managed according to HIPAA requirements. All subjects will sign a combined informed consent and HIPAA authorization form that includes specific privacy and confidentiality rights. Study data will be maintained per federal, state, and institutional data policies.

Authorized representatives of the following groups may need to review this research as part of their responsibilities to protect research subjects: representatives of the IRB and UWCCC (funding agency). The clinical study site will permit access to such records.

18. SHARING OF RESULTS

Each participant who undergoes cervical cancer screening after the workshop, either through clinician collection (if in the control) or self-collection (if in the intervention group), will be contacted by a CHW or other staff member of MCHH, and the participant's results will be given to her. Recommendations will be for all women to present in-person although if declines, results will be given via telephone. All results will also be mailed to the participant and preferred primary care provider (if applicable).

Dissemination of findings in this study will be made available in a journal that is yet to be determined although will be funded through the sponsor agency and in an open access journal. Authorship plans will include at minimum, Drs. [name], [name], [name], and [name] as authors, order of authorship to be determined. Subject's identity will remain confidential on presentation of data or publication.

19. DATA AND SPECIMEN BANKING

NA

20. STUDY ANALYSIS

20.1 Statistical Hypothesis

Participation in cervical cancer screening will be higher among women in the intervention group as compared to the control group.

20.2 Sample Size Justification

For this pilot study, we will enroll 250 participants, which is based on the feasibility of the number of workshops possible during the program length, funding, and resources available through MCHH.⁹ Power estimates are based on comparing the rate of participation between the intervention arm (participants offered self-collected hrHPV) and the control arm (participants offered clinician-collected screening). Estimates of screening rates for the Hmong women population (percent that have had a clinician-collected screening in the last 2-3 years) range from 61- 81%. As we do not have estimates for rates for Karen, Karen, Burmese, or Hmong women, we will use these estimates for participation rates in the control arm. The table below shows the detectable participation rates (and differences between proportions) for the intervention arm for different combinations of power (1- β) and values for the control arm from 0.61-0.81, for the hypotheses $H_0: P \leq p_0$ vs. $H_1: P > p_0$, where p_0 is the rate of participation in the control arm, for a sample size of 250 (125/arm), with a one-sided level 0.05 binomial test.

Control Participation Rate	Detectable Participation Rate (Difference)		
	0.80	0.85	0.90
0.61	0.77 (0.16)	0.78 (0.17)	0.79 (0.18)
0.71	0.85 (0.14)	0.86 (0.15)	0.87 (0.16)
0.81	0.93 (0.12)	0.93 (0.12)	0.94 (0.13)

As an example, if there is a participation rate of 0.81 for those offered clinician-collected screening, we will be able to detect a rate of 0.93 (a difference of 0.12) in the participants offered self-collected hrHPV with a one-sided level 0.05 binomial test with a power of 0.85.

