15. WITHDRAWAL OF PARTICIPANTS	20
16. DATA MANAGEMENT AND CONFIDENTIALITY	20
16.1 Project Data Collection	20
16.2 Data Storage and Maintenance	20
16.3 Confidentiality	20
17. Provisions to Protect the Privacy Interests of Participants	21
18. SHARING OF RESULTS	21
19. DATA AND SPECIMEN BANKING	21

20. STUDY ANALYSIS	21
20.1 Statistical Hypothesis	21
20.2 Sample Size Justification	22
20.3 Statistical Methods	22
21. POTENTIAL BENEFITS TO PARTICIPANTS	22
22. RISKS TO PARTICIPANTS	23
23. PROVISIONS TO MONITOR THE DATA TO ENSURE THE SAFETY OF THE PARTICIPANTS	23
24. ECONOMIC BURDEN TO PARTICIPANTS	23
25. RESOURCES AVAILABLE	23
26. MULTI-SITE RESEARCH	24
27. REFERENCES	24
28. APPENDICES	26

STATEMENT OF COMPLIANCE

I confirm that I have read this protocol. I will comply with the IRB-approved protocol, and applicable regulations, guidelines, laws, and institutional policies.

I agree to ensure that all staff members involved in the conduct of this study are informed about their obligations in meeting the above commitment.

Name	Signature	Date
Name	Signature	Date
[name]		08/08/23

[name]
Principal Investigator

SYNOPSIS

Study Title	Community Health Outreach to Increase Cervical Cancer Education and Self-Collection Screening (CHOICES) Program for Southeast Asian Immigrant and Refugee Women in Wisconsin
Brief Summary	The primary purpose of this study is to determine whether educational workshops paired with self-collected high-risk human papillomaviruses (hrHPV) screening will increase participation in cervical cancer screening among Southeast Asian refugee and immigrant populations in Wisconsin compared with offering clinician-collected screening (total sample size: 250 participants). We hypothesize that participation in cervical cancer screening will be higher among women in the intervention group as compared to the control group.
Number of study sites	1
Study Design	Workshops are randomized to either a control or intervention group.
Primary Objective	To evaluate whether educational workshops paired with self-collected hrHPV screening will increase participation in cervical cancer screening among Southeast Asian refugee and immigrant populations in Wisconsin compared with offering clinician-collected screening.
Secondary Objective(s)	To evaluate participant satisfaction with the educational workshops using satisfaction surveys.

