4. NUMBER OF PARTICIPANTS

Total number of study subjects: 250.

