11. STUDY INTERVENTION

This randomized controlled trial will be done in partnership with MCHH. Previous partnership with MCHH and UW-Madison researchers developed cervical cancer educational workshops designed by CHWs to provide innovative mixed-modality education consisting of pictographs, flipcharts, videos, and hands-on models. These workshops to be conducted in Hmong, Karen, and Burmese and Karen languages were tested in mock workshops with Hmong and Karen participants and through a community advisory panel prior to dissemination. This approach caters to the unique culture and communication styles of Southeast Asian immigrant and refugee populations.

All workshops will be conducted by the CHWs on the study team. If the CHW is not fluent in the target language (such as Karen or Burmese), then the CHW will conduct all study activities in English with a translator available to translate all activities.

All participants attending a workshop will be randomized as a group to either a control or intervention group. Workshops in the control group will provide education recommending standard of care (clinician-collected hrHPV testing and cytology screening). Workshops in the intervention group will be offered the same education with additional education on the option of self-collection (HPV testing only) for their screening method. All participants will have the same basic demographic information collected in MCHH's standard intake form with an additional question on current barriers to screening.

Participants will self-select which workshop day they would like to attend depending on their preferred language. Participants can attend any available date a workshop is being offered until filled. Participants will be blinded to knowing which workshops are control or intervention groups. Participants during consent will be made aware there are two different groups and the difference between the intervention and control group is the education provided and screening method offered at the end of the education session. Participants will be provided the full study details at the end of their participation.

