We anticipate a total of thirty workshops, fifteen of which will be control and fifteen of which will be intervention, will be planned in total over a sixteen-month period (Table 1). All workshops will have 8 participants recruited due to limited space of the community center, time, and to accommodate physical spacing needs. There will be two workshop sessions per day (one in the morning and one in the afternoon).

Table 1. Planned Number of Hmong and Karen Participants in the Intervention and Control Workshops

Intervention Workshop	1	2	3	4	5	Total
Hmong	8	8	8	8	8	40
Karen	8	8	8	8		36
Karen	8	8	8			24
Burmese	8	8	8			24
Control Workshop						
Hmong	8	8	8	8	8	40
Karen	8	8	8	8		36
Karen	8	8	8			24
Burmese	8	8	8			24

[figure not shown]
After workshop conclusion, participants will be offered same-day on-site cervical cancer screening depending on assignment in the control or intervention group (clinician-collected screening or self-collection screening, respectively). Participants, regardless of engagement in screening, will then complete a post-evaluation workshop survey (consisting of two surveys, see Appendix C).

Due to ethical concerns and our hypothesis that this population is less likely to do cervical cancer screening if offered clinician-collected screening only. Participants in the control workshops who answer “yes” on the survey to the question “If given the option, instead of having a clinician collect the sample, would you want to collect the sample on your own?,” will be subsequently offered self-collection for their screening method. CHWs will provide to these participants a 5-minute 1-on-1 instruction tutorial on self-collection, translated handout, private room to collect a sample, and then samples sent to the laboratory per protocol.

Similarly, participants will be made aware during the education of the self-collection method, that this is not a usual method that is offered in many clinical practices. If a participant were to visit their usual primary care doctor for an exam, a pelvic examination to obtain a clinician-collected cervical swab for HPV testing and pap smear is the usual method which they should anticipate. We are offering self-collection as studies show growing validity of HPV self-sampling, particularly among hard-to-reach populations.¹⁴⁻¹⁸ With this understanding, self-collection will be offered and encouraged although if participants desire clinician-collection instead this is option will also be made available.

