25. RESOURCES AVAILABLE

Will the research be conducted outside School of Medicine and Public Health or UW Hospitals and Clinics (e.g. the researcher does not have an SMPH research feasibility attestation for this study)?	 YES (complete 25.1)  NO (remove text below, but retain this section)
--	---

Feasibility of recruiting:

- Estimates of Hmong, Karen, and Burmese and Karen women in the Milwaukee area was calculated by using published data from 2019 by the Pew Research Center and population estimate of 50.52% in the US population are women.
- Number of Hmong women in the Milwaukee area age 30 to 64 is approximately 2001.
- Number of Burmese women in the Milwaukee area age 30 to 64 is approximately 1273.
- Estimate recruitment will be 80 Hmong, 48 Karen, 48 Burmese and 64 Karen women participants
- These are not true estimates of the number of women in the population we are recruiting from due to age and specific ethnicity. Inclusion of women in this study is between age 25-65 and Hmong, Karen, Burmese or Karen. Karen and Karen is a smaller ethnic group commonly grouped together with other ethnic groups categorized in the general Burmese ethnic group.
- Potential participants the research team has access to is not yet determined, although MCHH routinely recruits for and conducts educational workshops in which 368 participants were recruited between July 1, 2020 and June 30, 2021.
- Additional resources and networks will be provided through collaboration with the City of Milwaukee Health Department.

Personnel:

- All personnel who will engage in the study will have appropriate experience, credentials, and training.
- All personnel will have sufficient time available to conduct the research:
 - o Primary Investigator [name] will commit 5% of FTE to the research project.
 - o Collaborators [name] and [name] will commit 20% of FTE each to the research.
- All personnel will perform study activities commensurate with their job description and scope of practice and will be appropriately supervised and monitored.

Space and Facilities:

- Appropriate approvals and safeguards are/will be in place for both clinical and non-clinical space and facilities where study activities may occur. Type and risk-level of procedures have been accounted for when selecting space and facilities.

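### The plan gives inconsistent sample sizes: 250 women (125 per arm) for power, but 240 (120 per arm) from its own workshop schedule and recruitment estimate

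*Combined protocol and SAP*

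**What the plan says.** **250.** The synopsis brief summary gives "total sample size: 250 participants", and Section 4 gives "Total number of study subjects: 250". Section 20.2 says "we will enroll 250 participants, which is based on the feasibility of the number of workshops possible during the program length"; the same sentence adds funding and the resources of the community partner as further grounds. It then builds its table of detectable rates on 125 per arm with a one-sided binomial test at level 0.05. Its worked example is a control rate of 0.81 against 0.93, with power 0.85.

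**240.** Section 11 says "We anticipate a total of thirty workshops, fifteen of which will be control and fifteen of which will be intervention" and "All workshops will have 8 participants recruited due to limited space of the community center". The sample-size row of the synopsis reads 240. Section 25 says "Estimate recruitment will be 80 Hmong, 48 Karen, 48 Burmese and 64 Karen women participants", which also sums to 240.

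**248.** Table 1 in Section 11 prints row totals of 40, 36, 24 and 24 in each arm.

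Two other provisions bear on the point. Section 15 says "Subjects who sign the informed consent form and who do not attend the workshop will be replaced". On allocation, Section 11 says "All participants attending a workshop will be randomized as a group to either a control or intervention group".

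**The concern.** Section 20.2 is the only place where the plan says what the trial can detect, and its number of women does not match the workshops that are to supply them. The synopsis carries both totals. A reader cannot tell whether enrolment is complete at 240, 248 or 250, or which number the power statement describes. At stake are an unambiguous enrolment target and a power table that belongs to the trial as planned. The primary analysis and the feasibility of the trial are not in question.

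**Working it through.** **1. The totals**

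| Source | Calculation | Total | Per arm |
|---|---|---|---|
| Synopsis brief summary, Section 4, Section 20.2 | stated | 250 | 125 (Section 20.2) |
| Section 11 text | 30 × 8 | 240 | 15 × 8 = 120 |
| Table 1, from its cells | 5×8 + 4×8 + 3×8 + 3×8 = 40 + 32 + 24 + 24 | 240 | 120 |
| Synopsis sample-size row | stated | 240 | – |
| Section 25 | 80 + 48 + 48 + 64 | 240 | – |
| Table 1, printed totals | 40 + 36 + 24 + 24 = 124, times 2 | 248 | 124 |

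For comparison, 250/8 = 31.25 workshops, or about 15.6 per arm.

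Only the total of 36 separates 248 from 240. The rows hold 5 + 4 + 3 + 3 = 15 workshops per arm, as Section 11 states, so the row totalled as 36 has four workshops and 4 × 8 = 32. Section 25 agrees by elimination: 80 = 2 × 40, 48 = 2 × 24 (twice) and 64 = 2 × 32, whereas 2 × 36 would be 72.

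**2. Reproducing the Section 20.2 table at 125 per arm**

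The plan says only that the test is binomial. I took the one-sided Fisher exact test at level 0.05. Power is the sum, over all pairs (x1, x0) for which Fisher p ≤ 0.05, of Bin(x1; n, p1) × Bin(x0; n, p0). The detectable rate is the smallest two-decimal p1 whose power reaches the target.

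| Control rate | Printed rates for power 0.80 / 0.85 / 0.90 | Power at 125 per arm | Power at 124 per arm | Power at 120 per arm |
|---|---|---|---|---|
| 0.61 | 0.77 / 0.78 / 0.79 | 0.837 / 0.880 / 0.915 | 0.834 / 0.877 / 0.912 | 0.823 / 0.867 / 0.903 |
| 0.71 | 0.85 / 0.86 / 0.87 | 0.820 / 0.873 / 0.915 | 0.816 / 0.870 / 0.912 | 0.802 / 0.857 / 0.902 |
| 0.81 | 0.93 / 0.93 / 0.94 | 0.854 / 0.854 / 0.914 | 0.851 / 0.851 / 0.912 | 0.837 / **0.837** / 0.902 |

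At 125 per arm the printed rate is the smallest that meets its target in all nine cells, so the table is reproduced.

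**3. Moving to the other totals**

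At 124 per arm no cell changes. At 120 per arm eight cells still hold. The 0.81 row at power 0.85 does not: 0.837 < 0.85. The next two-decimal rate, 0.94, has power 0.902, so the cell becomes 0.94 (0.13). This cell is the worked example, so the two are one effect. Its power by women per arm is: 120, 0.837; 121, 0.841; 122, 0.844; 123, 0.847; 124, 0.851; 125, 0.854.

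**4. How much of this is rounding**

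Solving Fisher power = 0.85 for a control rate of 0.81 gives 0.9294 at 125 per arm and 0.9318 at 120 per arm. The underlying shift is 0.0024. It shows as 0.01 because the table gives the smallest two-decimal rate that reaches the target.

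**5. Dependence on the test**

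A pooled z-test (normal approximation, no continuity correction) would print 0.76/0.77/0.78, 0.85/0.85/0.87 and 0.92/0.93/0.94 at 125 per arm, matching four of nine cells. Under that test every printed cell still meets its stated power at 120 per arm: 0.853/0.892/0.923, 0.838/0.886/0.923 and 0.872/0.872/0.923. A continuity-corrected z-test matches eight of nine cells at 125 per arm. The one it misses is the worked example, for which it gives 0.842 against the stated 0.85.

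**The case against.** The strongest defence is that 250 need not be derived from the workshop count at all. Section 20.2 names program length, funding and resources too, and Section 11 only anticipates thirty workshops. A rounded enrolment ceiling slightly above 240 would be ordinary practice in a pilot. Section 15 replaces women who consent but do not attend, so 250 could be a count of consented women. This stands in part: a reader might infer that 250 is a failed multiplication of workshops by places, and the documents do not show that. They also do not offer either explanation, and Section 20.2 splits all 250 into two arms of 125 for the power calculation.

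The reverse inference, that exactly 240 women will enter the comparison, is not supported either. It needs every anticipated workshop to run and to be full, and Section 15 does not fix the number of attendees.

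On power, the test is inferred, and a pooled z-test leaves no cell short. Fisher remains the best reading because, of the methods tried, it alone reproduces the whole table. The certainty belongs to the mismatch in N and not to the single cell.

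On Table 1, the table has blank cells, was read from a PDF, and gives two groups the same label, so matching 64 to the four-workshop row is by elimination. Even so, the fifteen workshops per arm leave no place for a further session. A query to correct or explain the 36 is fair.

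Finally, randomization by workshop may matter more than the change from 125 to 120. With 8 women per workshop and an assumed intraclass correlation of 0.01, the design effect is 1 + 7 × 0.01 = 1.07, and 125/1.07 is about 117. That is true, but it is a separate issue and does not settle which N the plan means.

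**Conclusion.** The inconsistency is real and does not depend on any choice of test: 250 in three places, 240 in three others, and 248 from the printed totals of Table 1. Its consequence is minor. With a one-sided Fisher test, full workshops and women treated as independent, going from 125 to 120 per arm changes one cell of nine. The worked example's power falls from 0.854 to 0.837 against a stated 0.85, and its detectable rate rises from 0.93 to 0.94, of which the unrounded change is 0.0024. With a pooled z-test no printed cell falls below its stated power.

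A reader might go further and conclude that the trial is underpowered or needs more women. The documents do not support that on this point: the study is a pilot sized on feasibility, and the shortfall in the one affected cell is about 1.3 percentage points of power under an inferred test.

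**What to change.** 1. State one N in the synopsis (both places), Section 4, Section 11, Section 20.2 and Section 25. Either use 240 (120 per arm, 15 workshops of 8), or keep 250, say what it counts (for example, consented women including those replaced), and give the expected number of attendees as the basis for power.
2. Correct the two Table 1 totals of 36, or explain them if they are intended.
3. Name the test behind the Section 20.2 table.
4. Recompute the table and worked example at the chosen N. If that is 120 per arm with Fisher, the 0.81 row at power 0.85 becomes 0.94 (0.13). The example then reads either 0.81 versus 0.93 with power 0.84, or 0.81 versus 0.94 with power 0.90.
5. Add one sentence saying that these figures treat women as independent and make no allowance for randomization by workshop.

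The cost is a correction of text and tables, with no extra participants, workshops or data.

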20.3 Statistical Methods

20.3.1 Primary Outcome Measures and Analysis:

The primary outcome measure is uptake of cervical cancer screening. The results will be reported through summary statistics of the number of participants in each group subsequently engaging or seeking out cervical cancer screening either through services offered after workshop education or self-reported desire to follow up through their community health care provider. Comparisons between the study arms will be based on a binomial test. The analysis will indicate if participants offered additional self-collection education would be more willing to engage in cervical cancer screening. Summary statistics will also include uptake of screening differentiated by reported ethnicity.

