20.3.2 Secondary Outcome Measures and Analysis

Qualitative survey data will be obtained through pre- and post-workshop surveys to evaluate the impact of the educational workshops.

Further statistical support for this program will be obtained through consultation with statisticians in the UW-Madison SMPH and/or UW Carbone Cancer Center Biostatistics Shared Resource. For quantitative data, differences will be tested with Wilcoxon Rank-Sum tests for continuous or ordinal categorical data, Chi-Squared tests for unordered categorical data, and binomial tests for dichotomous data.

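### Sections 20.2 and 20.3.1 put the primary test in one-sample form while the power table matches a two-sample test; the two-sample test should be named

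*Combined protocol and SAP*

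**What the plan says.** All references are to the combined protocol and SAP.

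- **Section 20.2, hypotheses.** H0: P ≤ p0 against H1: P > p0, "where p_0 is the rate of participation in the control arm". The text does not say whether p0 is the unknown true rate, the observed rate or a fixed constant.
- **Section 20.2, test and size.** The detectable rates are given "for a sample size of 250 (125/arm), with a one-sided level 0.05 binomial test", over "values for the control arm from 0.61-0.81".
- **Section 20.2, aim of the calculation.** "Power estimates are based on comparing the rate of participation between the intervention arm" and the control arm. This is two-group language.
- **Section 20.3.1, primary analysis.** "Comparisons between the study arms will be based on a binomial test". Nothing more is said about the test.
- **Section 20.3.2, secondary analyses.** Wilcoxon rank-sum and chi-squared tests are named for other data types, and "binomial tests for dichotomous data".
- **Section 20.1.** The verbal hypothesis is that participation is higher in the intervention group than in the control group.
- **Section 11.** Everyone attending a workshop is randomised together, as one group.

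**The concern.** One unknown P set against a reference value p0, tested with a binomial test, is the standard notation for a one-sample problem. There p0 is known without error. Here the control rate is estimated from about as many women as the intervention rate. If the observed control proportion is inserted as p0, its sampling error drops out of the test and the false-positive rate rises.

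The wording is also at odds with the table printed next to it, which does not follow from a one-sample test. Someone running the analysis would have to work backwards from the table to learn which test was meant. Section 20.3.2 leaves further statistical support to later consultation, so the analyst may not be the author of 20.2. The choice between the two readings could then be made after the data are seen, and in some outcomes it decides whether the trial is called positive.

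**Working it through.** **Inputs.** From Section 20.2: n = 125 per arm, one-sided α = 0.05, control rates 0.61, 0.71 and 0.81, and the nine detectable rates. All calculations treat women as independent, as the plan's table does.

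**Step 1. Reproduce the plan's table.** For a two-sample test, power = Σ_c Σ_y Bin(c; 125, p_C) · Bin(y; 125, p_I) · 1[test rejects at (c, y)]. The one-sided Fisher test rejects when the hypergeometric tail probability is at most 0.05. Solving for p_I at each power:

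| Control rate | Power | Plan | Two-sample Fisher | One-sample, fixed p0, n = 125 |
|---|---|---|---|---|
| 0.61 | 0.80 / 0.85 / 0.90 | 0.77 / 0.78 / 0.79 | 0.7625 / 0.7728 / 0.7855 | 0.718 / 0.725 / 0.735 |
| 0.71 | 0.80 / 0.85 / 0.90 | 0.85 / 0.86 / 0.87 | 0.8467 / 0.8555 / 0.8662 | 0.809 / 0.816 / 0.824 |
| 0.81 | 0.80 / 0.85 / 0.90 | 0.93 / 0.93 / 0.94 | 0.9229 / 0.9294 / 0.9373 | 0.891 / 0.896 / 0.903 |

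Rounded up to two decimals, the Fisher column gives all nine of the plan's cells. For the worked example (0.81 against 0.93) its power is 0.854, and the plan states 0.85. The continuity-corrected two-sample formula, rounded up, gives eight of the nine. The one-sample column gives none. At the plan's nine rates a one-sample test would have power of 0.98 to 0.999, not 0.80 to 0.90. The table therefore already allows for sampling error in the control arm.

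**Step 2. Type I error of the literal form.** Suppose the control count is c and the analyst sets p0 = c/125, rejecting when P(Bin(125, c/125) ≥ y) ≤ 0.05. Summing the rejection probability over all (c, y) with equal true rates:

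| True common rate | Plug-in one-sample | Two-sample Fisher | Two-sample pooled z |
|---|---|---|---|
| 0.61 | 0.109 | 0.040 | 0.053 |
| 0.71 | 0.105 | 0.038 | 0.051 |
| 0.81 | 0.102 | 0.036 | 0.050 |

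With 120 per arm (15 workshops of 8, Section 11) the plug-in figures are 0.1045, 0.1086 and 0.1005. The large-sample limit shows why. The true variance of the difference is twice the variance that the test uses, so the error is 1 − Φ(1.645/√2) = 1 − Φ(1.163) = 0.122. The exact test is somewhat below this because counts are discrete.

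**Step 3. Can the reading change the result?** Take 89 of 125 control women screened (71%). The plug-in test first rejects at 98 of 125 in the intervention arm (p = 0.044). Fisher does not reject at 101 (p = 0.051) and first rejects at 102 (p = 0.037). For 98 to 101 intervention successes, the reading of the test's name decides the conclusion.

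**The case against.** The best case for the plan is that it means a two-sample test and only words it loosely. Section 20.1 states a two-group hypothesis, 20.2 speaks of comparing arms of 125 and of differences between proportions, and 20.3.1 speaks of comparisons between arms. A test against a fixed constant would need no control participants. If p0 is read as the unknown control-arm rate, H0: P ≤ p0 is simply p_intervention ≤ p_control. Step 1 supports this reading.

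That argument stands against a stronger claim that a reader might infer: that the plan's test ignores control-arm sampling error and so doubles the type I error. The documents do not support it. Nowhere do they tell the analyst to treat the observed control rate as known, and the power figures are not those of a one-sample test. The inflation in Step 2 belongs to one possible execution of the wording, not to a procedure that the plan prescribes.

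The argument does not remove the ambiguity. No two-sample test for a binary outcome is named in 20.2, 20.3.1 or 20.3.2, and the wording as it stands permits a test that conflicts with the plan's own table.

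A second fair objection is that moving to a workshop-level test goes beyond the one-sample question. That is true: Fisher's test alone would settle the wording. But once the test is being named, it makes sense to name one that fits the randomisation in Section 11.

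**Conclusion.** The concern holds as a defect of specification, and it should be corrected before analysis. The hypothesis and test are written in one-sample form, while the stated power matches a two-sample one-sided Fisher test at 125 per arm. If the literal form were run with the observed control rate as p0, the one-sided type I error would be about 0.10 to 0.11 instead of 0.05 at control rates of 0.61 to 0.81.

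This figure is conditional on that execution and on independent women. The match to Fisher relies on rounding up, so the table points clearly to a two-sample method but does not prove which one was used. The effect of workshop clustering is not included in any figure here.

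**What to change.** 1. **Section 20.2.** Write H0: p_intervention ≤ p_control against H1: p_intervention > p_control, and state that both rates are estimated from the trial.
2. **Section 20.3.1.** Replace the binomial test with a named two-sample test. Preferably use a one-sided permutation test or t test on workshop uptake proportions, stratified by language. A permutation test should follow the randomisation actually used. Report the difference in uptake with its confidence interval.
3. **Section 20.3.2.** Replace the binomial tests with a named two-sample test.

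**Cost.** The text changes are a few sentences. One-sided Fisher's test would leave the power table unchanged but would still treat women in the same workshop as independent. A workshop-level test means restating the table for clustering. The plan gives no within-workshop correlation, so a range would have to be assumed.

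Workshop-level analysis of survey items also needs one added field. Sections 13.1.3.2 and 16.2 keep survey responses unlinked to the study ID, and the form in Appendix C records the type of education but not which workshop was attended. This affects the primary outcome too: Section 20.3.1 counts self-reported desire to follow up, and the questions on future screening are in survey Sections C and G. A workshop code would supply the link without a study ID. The same code is worth holding with the uptake data, because Section 16.2 lists only the workshop date and Section 11 plans two sessions per day.
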